Protocol: AAAF1797

Principal Investigator: [name]

Title: Randomized controlled trial of Vitamin D Repletion Regimens in Primary Hyperparathyroidism

Study Purpose and Rationale:

Vitamin D deficiency is very common in the setting of PHPT, and leads to higher PTH levels. In this study, we will investigate the impact of two different vitamin D repletion regimens over a six month period in patients with PHPT and concurrent vitamin D deficiency. We hypothesize that vitamin D repletion ameliorates the extent of hyperparathyroidism and improves biochemical, microarchitectural and biomechanical features of the disease. In addition, we will show that vitamin D can be repleted safely in patients with PHPT. This would be of great importance to the many physicians treating patients with PHPT today, who are being advised to replete vitamin D in these patients without any clear guidelines as to how best to do so.

Study Design:

40 patients with PHPT and vitamin D deficiency (25OHD less than 30 ng/ml) will be enrolled and randomized 4:1 to two different vitamin D repletion regimens. Randomization to treatment will use randomly permuted blocks. Our first group will receive 2 capsules of 10,000 IU of vitamin D once per week for the first month and then 1 capsule of 10,000 IU of vitamin D once per week for the remaining five months which should replete vitamin D deficiency and decrease PTH (our primary end-point). Control subjects (Group 2) will take 2 capsules of the placebo once per week for the first month and then 1 capsule of the placebo once per week for the remaining five months. All subjects will receive 400 IU of vitamin D each day, either in the form of a multivitamin or by itself, for the entire study. Our protocol provides 400 IU of vitamin D per day for control subjects because we felt that ethically it would not be appropriate to withhold all vitamin D from this group. A 400 IU dose is expected to raise serum 25-OHD levels minimally (2-3 ng/ml) thus allowing this cohort to serve as a valid control group ¹.

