measure will use linear mixed models for repeated measures to assess the fixed effects of vitamin-D repletion regimen, time, regimen time interaction, random effects for intercept and standard covariates; and a covariance structure fit prior to the hypothesis test. Average time to achieve a 25-OHD level of 30 for the two vitamin-D repletion regimens will be estimated with a Cox proportional hazards model. Power and sample size calculations assume PTH is analyzed in log units, unequal sample sizes in the two groups, unequal variances in the two groups, a type I error rate of 0.05, 80% power and a two-tailed T-Test of the post-treatment PTH levels. A reduction in the treated group from 149 ± 64 ng/ml to 85 ± 48 pg/ml is larger than our original estimated effect size but consistent with the data available from our cross-sectional study for patients with 25OHD 30 ng/ml, respectively. Given the above assumptions and a desired 4:1 treatment allocation ratio, a sample size of 40 distributed 32 vs 8 meets our power goal (calculated with harmonic mean sample size of 13 per group). The analysis of safety event rates will include Fisher's Exact comparisons of between-group differences in the number of patients with hypercalcemia and/or hypercalciuria; and a Cox proportional hazards assessment of time to first AE adjusted for standard timeindependent covariates and time-dependent cumulative vitamin D dosage will be used to estimate the contribution of vitamin D to the development of the safety events. Assessments of safety events will be conducted to relate the onset of safety events to baseline vitamin-D levels, to the ramp of vitamin-D level increase and peak available vitamin-D level at time of event (to the extent known). Standard covariates for all analyses include season, weight, serum calcium and age. All power and sample size calculations based on SAS Power and Sample Size 3.1 (SAS Institute, Cary, NC).

References:

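### The secondary safety Cox model fits 5 to 7 terms to at most 40 first events, and its undefined AE endpoint does not match its stated purpose

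*Combined protocol and SAP*

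**What the plan says.** Statistical Procedures specifies a Cox analysis of "time to first AE adjusted for standard timeindependent covariates and time-dependent cumulative vitamin D dosage" and says that it "will be used to estimate the contribution of vitamin D to the development of the safety events". The same section names season, weight, serum calcium and age as the standard covariates for every analysis. The design has "a sample size of 40 distributed 32 vs 8", justified only by the PTH endpoint.

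Four things are not stated: what counts as an AE, how season is coded, how many events are expected, and what happens if events are too few to fit the model.

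This model is not the only safety analysis. Statistical Procedures also plans Fisher's exact tests on hypercalcemia and hypercalciuria, and assessments of event onset against baseline vitamin D level, its rate of rise and its peak. Study Design plans between-group comparisons of outcome frequencies at each time point. It names the monitored outcomes as serum calcium above 12 mg/dL, nephrolithiasis, and urinary calcium above 400 mg/day.

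**The concern.** Showing that vitamin D can be repleted safely in this population is a stated aim, and this is the only specified model that ties event timing to vitamin D exposure. Two features weaken it.

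- **Size.** The number of terms is large for 40 patients. When events are few, a Cox partial likelihood can keep rising as a coefficient goes to plus or minus infinity. Software then reports a meaningless estimate with a huge standard error, or does not converge.
- **Target.** The endpoint is the first AE, but the purpose refers to the safety events. If AE means any adverse event, a patient whose first AE is unrelated leaves the risk set, and a later calcium event does not enter this model.

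The risk is that an unstable or mis-targeted hazard ratio is read as reassurance.

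**Working it through.** **The plan's own figure.** The harmonic mean of 32 and 8 is 2 × 32 × 8 / 40 = 12.8, which rounds to the stated 13. With the stated PTH means and SDs (149 ± 64 and 85 ± 48), log scale and SD taken as the coefficient of variation, an unequal-variance t-test at 32 vs 8 has 81.8% power. So N = 40 is reproduced for PTH. No corresponding figure exists for the safety model.

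**Terms.** Weight, serum calcium, age and cumulative dose give 4. Season adds 3 if it has four levels and 1 if it has two. The total is 7 or 5. The ceiling on events per term is 40/7 = 5.7 or 40/5 = 8.0.

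**Reading A: AE means the monitored calcium and stone events.** The documents give no event rate, so the six-month risk is assumed over a range. Expected events = 40 × risk, and P(no control event) = (1 − risk)^8. The non-finite shares come from simulation: 32 vs 8, the protocol dose schedule, constant hazard, no true effect, independent covariates and no dropout. Ranges reflect separate simulations with adherence either varying (SD 0.1) or identical between patients.

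| Assumed risk | 10% | 20% | 30% | 50% |
|---|---|---|---|---|
| Expected events | 4 | 8 | 12 | 20 |
| Events per term, 7 terms | 0.6 | 1.1 | 1.7 | 2.9 |
| Events per term, 5 terms | 0.8 | 1.6 | 2.4 | 4.0 |
| P(no control event) | 43% | 17% | 6% | 0.4% |
| Any coefficient non-finite, 7 terms | about 86% | 40-50% | 16-21% | 1-3% |
| Dose coefficient non-finite, 7 terms | 20-53% | 1-16% | 0-7% | under 1% |
| Any coefficient non-finite, 5 terms (varying adherence only) | 27% | 4% | 0.2% | 0% |

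Grouped by observed events, the share of trials with any non-finite coefficient is as follows.

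| Events | 7 terms | 5 terms |
|---|---|---|
| 1-4 | 97-98% | 49-81% |
| 5-8 | 60-69% | 4-32% |
| 9-12 | 19-34% | 0-18% |
| 13-20 | 2-13% | 0-7% |
| 21-40 | under 1% | under 1% |

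Season is the usual cause. With 10 patients in each of four seasons and 4 events, the chance that every season has an event is 10^4 / C(40,4) = 10,000 / 91,390 = 11%, so some season is empty in 89% of cases. By simulation, that share is 30% at 8 events, 6% at 12 and 0.1% at 20. The dose coefficient diverges mainly with very few events, or when no control has an event and adherence is uniform.

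**Reading B: AE means any adverse event.** Let c be the calcium-event risk and b the unrelated-AE risk, with independent exponential times, lc = −ln(1 − c) and lb = −ln(1 − b). The share of calcium events that follow an unrelated AE is [c − lc/(lb + lc) × (1 − exp(−(lb + lc)))] / c.

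- c = 0.20, b = 0.20: lc = lb = 0.223, so (0.20 − 0.5 × 0.36) / 0.20 = 10%.
- c = 0.20, b = 0.80: lb = 1.609, so (0.20 − 0.122 × 0.84) / 0.20 = 49%.

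Both b values and c are assumptions.

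**What any model can deliver here.** Unadjusted Schoenfeld power at 4:1 for a hazard ratio of 3 is Φ(√(d × 0.8 × 0.2) × ln 3 − 1.96). This gives 24% at d = 8 events, 50% at 20 and 79% at 40.

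**The case against.** Several points on the other side are sound.

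- **The two weaknesses cannot both be at their worst.** Counting any AE raises the event count. A 10% calcium-event risk with unrelated AEs in 20-80% of patients gives any-AE risks of 1 − 0.9 × 0.8 = 28% to 1 − 0.9 × 0.2 = 82%, or about 11 to 33 first events. Non-finite fits are then much less common. This stands, and the two readings must be treated as alternatives.
- **A reader might infer that the model will often yield no estimate.** The documents do not support that. They give no event rate and no season coding. Two season levels cut the failure share sharply, and above 20 events it is under 1% either way. A diverging season term also need not spoil the dose estimate.
- **A reader might infer that the safety question goes unanswered.** It does not. Fisher's tests, the frequency comparisons and the assessments of level, rate of rise and peak are all planned, and a calcium event that follows an unrelated AE is still available to them. They are weak (with 0/8 control events, 13/32 treated events are needed for p < 0.05), and the level assessments have no stated model, but they exist. They do not repair this model.
- **A reader might infer that cumulative dose is the wrong exposure.** The between-arm difference grows from 20,000 IU at week 1 to 4 × 20,000 + 22 × 10,000 = 300,000 IU at week 26, so a linear term implies a 15-fold growth in the log hazard ratio. That is a modelling preference. Cumulative dose is a legitimate metric, and the plan examines rapid change separately.
- **AE may be shorthand for the safety events.** Possibly, since the sentence begins and ends with that term. Then the sparse-event reading applies. The supportable criticism is that the term is undefined.

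**Conclusion.** The point holds as a weakness in one secondary model. The safety Cox model is over-parameterised for 40 patients with 8 controls, its endpoint is not tied to its purpose, and no sparse-event fallback is stated. Under the narrow reading of AE, instability is substantial at assumed risks of 30% or less with a four-level season, and much smaller with a two-level season. Under the broad reading, the fit is steadier but the model does not estimate vitamin D's contribution to the safety events. Only the term count and the ceiling of 40 events come from the documents. The event risks, unrelated-AE rates, season coding and adherence pattern are assumptions. A cheap change to the plan's wording gives a better method, so it should be made, but the trial's safety evaluation as a whole does not depend on it.

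**What to change.** Amend the safety paragraph of Statistical Procedures as follows.

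1. Define the event as the first of the hypercalcemia, hypercalciuria or nephrolithiasis outcomes that Study Design already monitors.
2. Fit a Firth-penalised Cox likelihood with profile-likelihood intervals, and at most one baseline covariate named in advance.
3. Report the randomised-arm comparison alongside the cumulative-dose model.
4. Report other AEs as counts by group.
5. State that intervals are the main result, and that a null result will not be read as evidence of safety.

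In simulation, a Firth fit with arm plus one covariate gave no non-finite estimates and a type I error of 3-7% at 10%, 20% and 30% risk. That rests on about 250 runs per setting, where the Monte Carlo standard error is √(0.05 × 0.95 / 250) = 1.4 percentage points. The cumulative-dose version was not simulated.

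The cost is wording and standard software options; no data collection changes. There are two downsides: less covariate adjustment, and fewer events than an any-AE endpoint, so power stays low (24% at 8 events and 50% at 20 for a hazard ratio of 3).
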